12.4 Randomisation methods

Randomisation will be conducted by the research fellow contacting a central randomisation service (Sealed Envelope™) after the patient has provided informed consent and baseline data (Class A method of randomisation).

Patients will be randomised using a 1:1 ratio from a computer-generated permuted block system of variable sizes. Stratification will take place by site and each patient will be randomised to one of the two treatment groups on an individual basis.

Randomisation will further be stratified according to the type of inclusion criteria (persistent symptoms or raised CRP).

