No clinical screening or trial procedures will be conducted prior to taking consent from the participant. Consent will not denote enrolment into trial. All patients screened will be recorded on the screening log, along with a screening number. Those patients who are enrolled into the trial will be allocated a formal trial identifier at the point of randomisation, and this will be the study number used to identify them for all subsequent study procedures.

Randomisation and Blinding

- Randomisation will take place according to the trial specific randomisation SOP.

- Sealed Envelope[™] (www.sealedenvelope.com) will be responsible for the randomisation process including production of the randomisation list. The randomisation list will be held by Sealed Envelope[™] until data lock.
- Randomisation of patients will be conducted by delegated member of the research team at the sites using an internet randomisation service provided by Sealed Envelope, at visit 1 (screening visit) (if patient is eligible for the study following assessment of results), and after the patient has provided informed consent and baseline data (Class A method of randomisation).
- Patients will be randomised equally into the treatment (ciprofloxacin) or control (placebo) group (1:1 randomisation) using a computer-generated permuted block system of variable sizes, stratified by site and presence or absence of symptoms (as defined by any one or more of persisting breathlessness, increased sputum volume, increased sputum colour. This will be assessed by the standardised symptom questionnaire detailed in section 8.4).
- Upon randomisation, patients will be allocated a trial number and will be given a study specific patient card, which will have the study title, IMP details, patient trial number and the contact details of the PI/CI/research team and out of hours contact details in cases of emergency.
- Randomisation details will also be entered on to the trial subject log held in the site file.
- Following the randomisation process and the generation of a randomisation number, pharmacy at the research sites will be notified by an automatic email. The research fellow will give the study medication to the patient at the screening visit.

Study variables and endpoints

(i) Each centre provides information on patients not randomised into the trial (overall number, reasons for exclusion).

(ii) For randomised patients, baseline data are collected for a variety of characteristics, including

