The primary outcome is the time to the next exacerbation within the 90-day study period. This will analysed using Cox proportional hazards regression, stratified by centre. The estimated hazard ratio between the groups will be reported, along with its 95% CI. A Kaplan-Meier plot will be produced. Patients who do not suffer a recurrent exacerbation during follow-up will be treated as censored observations at their end of follow-up time. As analysis is intention to treat, non-compliers will be

treated as belonging to the treatment group originally randomised to. Where patients withdraw from follow up, every effort will be made to ascertain their primary outcome (i.e. date of next exacerbation OR exacerbation-free survival to 90 days) by telephone. We will adjust only for number of exacerbations in previous year and centre in this primary analysis.

Variables:

Time until event or censoring: excn.or.cens.d
 surv1 <- coxph(Surv(time, cens) ~ arm

A supporting analysis will be undertaken that adjusts for site and patient selfreported history of exacerbations in the previous year.

- o **site:** site
- Excns in previous year: prev.excns
- Arm: [not yet released]

surv1 <- coxph(Surv(time, cens) ~ arm + strata(site) + prev.excns)</pre>

An additional supporting analysis will be undertaken, additionally adjusting for baseline covariates age; sex; FEV1% predicted; SGRQ total score; number of exacerbations in previous year; whether hospitalised for index exacerbation; whether index exacerbation was treated with steroids in addition to antibiotics; whether included due to symptomatic or inflammatory criteria, and smoking status. This will be for hypothesis generation only. It will not be used to come to overall conclusions regarding treatment efficacy; this will be treated as a secondary analysis.

- Age (continuous): *age.cts*
- Sex: sex
- FEV1% predicted at baseline: fev.pred
- SGRQ total score at baseline: *sgrq1.total*
- **Hospitalised for index excn (y/n):** *hospital.yn*
- Index excn treated with steroids (y/n): *steroids.given.yn*
- Included due to symptomatic criteria or inflammatory criteria [to be queried]
- Smoking status: curr.smok

surv2 <- coxph(Surv(time, cens) ~ arm + strata(site) + prev.excns + age.cts + sex + fev.pred +
sgrq1.total + hospital.yn + steroids.given.yn + XXX[inclusion crit.] + curr.smok, data=wp4)</pre>

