The percentage of missing data will be summarised and spurious data double checked as far as possible. Primary analysis will be intention to treat, and so every effort will be made to collect all follow-up data from non-compliers and patients who discontinue treatment. All patients will be analysed from the date of randomisation until end of follow-up period or the date of drop-out. The primary analysis will therefore assume patients who drop-out of the trial do so 'at random'.

Secondary outcome analysis

For each secondary outcome, two analyses will be undertaken – the first adjusting for centre and the baseline value of the endpoint being analysed (where available), and the second also taking into account the additional baseline characteristics specified in the supporting analysis of the primary outcome above.

When modelling continuous data, transformations will be undertaken as necessary to normalise the data. Where appropriate, analyses will take account of length of follow up as an offset, and also account for differences in at-risk periods. Summary measures of the secondary outcomes will be presented (mean, standard deviation, median, interquartile range for continuous variables, percentages for categorical variables) by treatment group and for both baseline and end of trial follow-up visits. The percentage of missing data will be summarised.

Secondary outcomes

- Time until *resolution* of first exacerbation will be compared between the active treatment and placebo groups, using Cox proportional hazards regression, stratified by centre.

• Duration of first exacerbation: dur

- The number of treatment-related adverse events will be analysed by using negative binomial regression. Negative binomial regression models collapse to Poisson regression if there is no overdispersion.

• Number of treatment-related AEs: trt.rltd.aes

- Exacerbation frequency: The rate of exacerbations experienced during the study period per person-year will be analysed by using negative binomial regression.

• Number of exacerbations: excns

- Frequency of antibiotic courses: The rate of antibiotic courses received for patients in the active treatment and placebo groups will be compared using negative binomial regression.

- The rate of hospital attendances during the study period will be analysed by negative binomial regression. .

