- Changes in respiratory healthcare status, assessed using SGRQ. SGRQ (score between 0 and 100from baseline to day 90 will be modelled as a normally distributed random variable. Linear regression will be used,

- Changes in respiratory healthcare status, assessed using CAT. CAT (score between 0 and 40) from baseline to day 90 will be modelled as a normally distributed random variable. Repeated measures analysis will be used to assess treatment effects over time during the follow-up period.

- Lung function: Changes in FEV1, FEV1 as % predicted, and FEV1/FVC ratio and FVC at day 90 from day 0 will be modelled separately as continuous outcomes and assumed to be normally distributed. Repeated measures analysis will be used to assess treatment effects over time during the follow-up period.

- Change in CRP from study entry to 90 days will be modelled as a normally distributed random variable. Repeated measures analysis will be used to assess treatment effects over time during the follow-up period.

- Resistance patterns (not resistant, resistant) will be analysed using logistic regression.

- The change in (log10) bacterial load from trial beginning to end will be analysed using parametric survival regression(linear regression with censored outcome data). Values below limits of detection will be treated as left censored.

- Adherence as assessed by pill counts. The number of pills taken over total number dispensed will be modelled using logistic. The difference in percent adherence will be assessed between treatment groups.

- Cost-effectiveness will be assessed as part of a future study (WP5)

This study is not powered to test these secondary outcomes – only the primary outcome. As such, analyses of the secondary outcomes will be hypothesis generating only.

Subgroup analyses

Relevant subgroups may be analysed (including patients who gave sputum samples), allowing the incorporation of any important new information and methodological concerns identified between now and the time of writing the analysis plan. However, such analyses should be undertaken before unblinding, and keeping in mind that any analyses will be hypothesis generating only.

Sensitivity analysis

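### The SAP contradicts itself on which model is primary, and neither reading includes the second randomisation factor

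*SAP*

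**What the plan says.** **Allocation.** The SAP (Randomisation and Blinding) and protocol 8.2 both describe permuted blocks "stratified by site and presence or absence of symptoms". Protocol 12.4 words the second factor differently: "Randomisation will further be stratified according to the type of inclusion criteria (persistent symptoms or raised CRP".

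**Primary model.** The SAP (Primary outcome analysis) specifies a Cox model stratified by centre and adds: "We will adjust only for number of exacerbations in previous year and centre in this primary analysis". A code line follows that contains only `arm` and has no closing bracket. The next paragraph reads "A supporting analysis will be undertaken that adjusts for site and patient selfreported history of exacerbations in the previous year", with the code "surv1 <- coxph(Surv(time, cens) ~ arm + strata(site) + prev.excns". A further supporting model adds other baseline variables. Its nearest term to the second factor is listed as "Included due to symptomatic criteria or inflammatory criteria [to be queried" and coded as `XXX[inclusion crit.]`.

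**Secondary models.** There are two per outcome, "the first adjusting for centre and the baseline value of the endpoint being analysed (where available" and a second that adds the further covariates. The SAP also says that "analyses of the secondary outcomes will be hypothesis generating only".

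**Protocol 12.3.2.** The hypothesis is tested by log-rank. The analysis adjusts for sex, phenotype, CAT, CRP, lung function, previous-year exacerbations and admission for the index event.

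**The concern.** The SAP states that its purpose is to clarify the primary analyses and to avoid misleading post-hoc inference. A primary model with two labels defeats that purpose, because the p-value that decides the trial could be chosen after the data are seen. Only the additional supporting model is expressly barred from driving the overall conclusion. Nothing rules out either of the first two.

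Separately, an analysis normally carries the factors that constrained the allocation. If a prognostic stratification factor is left out, the standard error is slightly too large for the balance achieved, so the test is conservative and some power is lost. Here one of the two factors is carried and the other dropped, with no explanation.

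**Working it through.** **1. The statements side by side**

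| Place | Model | Label |
|---|---|---|
| SAP primary text | arm, centre, previous exacerbations | primary |
| SAP first code line | arm, then breaks off | placed under the primary text |
| SAP next paragraph and code | arm, `strata(site)`, `prev.excns` | supporting |
| SAP additional model | the above plus further covariates, including the undefined inclusion term | secondary, hypothesis generating |
| Protocol 12.3.2 | log-rank test; Cox with seven covariates | primary |

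Rows 1 and 3 are the same model under opposite labels. Both labels stand in complete sentences, so the conflict does not depend on the broken code line. The second randomisation factor is absent from rows 1 to 3.

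**2. The SAP's own power figures**

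Inputs (SAP, Sample size): N = 138, 5% dropout, placebo exacerbation-free proportion 0.45. Two-sided 5% comes from protocol 12.2.1. After dropout, 138 × 0.95 = 131.1.

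- HR 0.46: treated proportion 0.45^0.46 = 0.693. Events = 131.1 × (0.55 + 0.307)/2 = 56.2. Freedman: √56.2 × 0.54/1.46 − 1.96 = 0.81, power 79.2% (stated 80%).
- HR 0.39: 53.6 events, power 89.5% (stated 90%).

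Both reproduce. Neither uses covariates, so no sample size changes.

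**3. Cost of leaving the factor out**

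Cox simulation with the SAP inputs, HR 0.46, blocks within site × symptoms, 15,000 trials per scenario. Assumed, not in the documents: four sites split 50/25/15/10% with hazard ratios 1/1.2/0.9/1.1; a negative binomial previous-exacerbation count with mean 2.5 and hazard ratio 1.15 per event; and the symptom hazard ratio.

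The lowest symptomatic share comes from the SAP's recruitment figures: 0.6 × (350 − 115) = 141, and 141/256 = 55%. If half of the 115 raised-CRP patients also have symptoms (assumed), it is (141 + 57.5)/256 = 78%.

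Power without the factor / as a covariate / as an extra stratum:

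| Symptom HR | 55% symptomatic | 78% symptomatic |
|---|---|---|
| 0.67 | 0.816 / 0.823 / 0.814 | 0.818 / 0.824 / 0.811 |
| 1 | 0.823 / 0.823 / 0.814 | 0.824 / 0.825 / 0.814 |
| 1.5 | 0.811 / 0.820 / 0.810 | 0.819 / 0.821 / 0.815 |
| 2 | 0.807 / 0.826 / 0.819 | 0.810 / 0.821 / 0.814 |
| 3 | 0.787 / 0.831 / 0.823 | 0.798 / 0.824 / 0.820 |

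The covariate gains 0 to 0.9 points for symptom HR 0.67 to 1.5, and about 1 to 4.4 points for HR 2 to 3. The extra stratum loses up to 1 point (0.824 to 0.814) in the first range. Type I error is 3.5 to 5.2% without the factor and 4.8 to 5.4% with it. For symptom HR up to 2, the average treatment HR is 0.452 to 0.465 without and 0.450 to 0.454 with. A second simulation (share 60 to 90%, symptom HR 1.5 to 3) gave gains of 0.4 to 3.9 points.

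**4. Cost of the ambiguity**

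Share of trials in which arm-only and site + previous-exacerbations disagree on p < 0.05. Assumed: mean count 2.5, dispersion 1.5; 3,000 trials.

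| HR per previous exacerbation | True HR 0.46 | True HR 0.62 |
|---|---|---|
| 1.0 | 2.9% | 4.2% |
| 1.15 | 7.8% | 10.9% |
| 1.3 | 15.5% | 17.5% |

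Under the null each model alone rejects in 4.7 to 5.4% of trials; taking whichever is significant rejects in 5.5 / 6.7 / 7.3%. The rates depend on the assumed count distribution. At HR 0.46 and 1.15 per event, another run gave 3.6% (Poisson), 4.6% (size 4) and 8.4% (size 1.5). If the broken line in fact ended in `strata(site) + prev.excns`, disagreement is 0%.

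**5. The placeholder variable**

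Protocol 6.1 admits patients on symptoms, CRP or both. From the SAP's figures, between 0 and 115/256 = 45% could meet both. A two-level symptomatic-or-inflammatory variable cannot code them.

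**The case against.** The first code line is visibly incomplete, and a line broken in PDF reading is not an error in the plan. If it matched the text, no arm-only model exists and the disagreement rates vanish. That stands, and the rates are therefore conditional. It does not remove the label conflict.

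The SAP's wording suggests that the primary adjustment was kept short on purpose, and a related term appears in the additional supporting and second-level secondary models. The omission costs at most about a point of power unless symptoms are strongly prognostic. That also stands: this half is modest, and the SAP lacks a reason rather than a valid test.

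It is also fair that the secondary models were not simulated and are exploratory, so the gap there is one of consistency only.

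Three stronger readings are tempting. A reader might infer that omitting the factor invalidates the test or inflates type I error; the simulation shows the opposite direction. A reader might infer that the SAP's primary model is definitely unadjusted; the broken line cannot carry that. A reader might infer that protocol 12.4 is simply the wrong wording; the documents do not show which definition the randomisation system used.

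**Conclusion.** The concern holds in two parts of unequal weight.

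The main part is the contradiction over the primary model, together with the unreconciled covariate list and log-rank test in protocol 12.3.2. This is established from the text alone. Its numerical effect is not: roughly 3 to 18% of trials under the assumptions tried, driven by the assumed strength and spread of previous exacerbations, and zero if the code matched the text.

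The lesser part is the omitted randomisation factor, under either wording of it. It makes the test slightly conservative. The power cost is about 0 to 1 point for an assumed symptom HR of 0.67 to 1.5, and up to about 4 points only for 2 to 3. The documents give no symptom hazard ratio, so these are ranges, not estimates. The plan should be corrected, but its stated power and sample size are not called into question.

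**What to change.** Before unblinding:

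- Confirm from the randomisation system which second factor was used, then reconcile protocol 8.2, protocol 12.4 and the SAP to it.
- State one primary model, identical in text and code: `coxph(Surv(time, cens) ~ arm + strata(site) + [second randomisation factor as recorded at randomisation] + prev.excns)`. Enter the factor as a covariate, not as a further stratum.
- Label every other model as supporting.
- Replace `XXX[inclusion crit.]` with symptoms yes/no and CRP ≥8 mg/L yes/no, so that patients meeting both criteria are coded.
- State that this model supersedes the covariate list and log-rank test in protocol 12.3.2.
- Optionally, for consistency, add the same covariate to the first-level secondary models.

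The cost is one covariate, corrected labels and code, and one check of the randomisation set-up. Symptoms and CRP are already recorded at screening, and the SAP lists the arm variable as not yet released.

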3.2 Clinical data, Rationale and Risks/Benefits

COPD exacerbations are episodes of increased respiratory symptoms such as increased shortness of breath, increased sputum purulence and increased sputum volume (3). Oral corticosteroids are prescribed if exacerbations are associated with adverse effects on daily activities (4, 5). Antibiotics are normally used to treat COPD exacerbations in the event of associated sputum purulence or increased sputum volume and are associated with faster resolution of the exacerbation and delayed time to the next exacerbation (6).

A recent study has shown that treating a single exacerbation prolongs the time to onset of subsequent exacerbations and reduces mortality (7).

We have shown that following a first exacerbation, 27% of COPD patients will have another exacerbation within 8 weeks (8). In this study we also showed that it is these recurrent exacerbations that drive exacerbation frequency and thus there is a need to prevent their occurrence. The importance of recurrent exacerbations is highlighted by the finding that once a COPD patient is discharged from hospital they are at 34% risk of subsequent exacerbations in the following three months, with significantly increased mortality (9). This indicates an urgent need to validate interventions in this high-risk period after the initial exacerbation to reduce the likelihood of a second exacerbation.

We also reported that a raised serum C-Reactive Protein (CRP) concentration measured 14 days after a first exacerbation is predictive of a second exacerbation within 50 days, suggesting that failure to normalise the inflammatory response may predispose to another (recurrent) exacerbation (10).

Following an exacerbation, patients are often not regularly assessed for non-recovery or recurrence and this may contribute to the high morbidity and readmission rates after exacerbations. At present, there are no studies investigating further treatment for patients after a first exacerbation who have

failed to recover and/or normalise the inflammatory response, and are therefore at heightened risk of a subsequent event. Our aim in this study is to address this question in high-risk patients and test a novel approach to reducing the risk of subsequent exacerbation and speeding recovery.

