6.1 Inclusion criteria

Patients eligible for enrolment in the study must meet all the following criteria:

- Pre-existing diagnosis of COPD confirmed by post-bronchodilator FEV1/FVC ratio of <0.7 at screening
- Severity of disease: Patients with a measured FEV1 < 80% of predicted normal values
- Evidence of COPD exacerbation treated 14 days prior to study enrolment (as defined by an episode of treated symptomatic worsening of COPD which is documented in the case notes or referral letter and/or confirmed with the treating clinician) with 5-14 days of non-quinolone antibiotics
- Age: ≥ 45 years of age at screening.
- Measured CRP (C-reactive protein) ≥ 8mg/L AND/OR persistence of one or more major symptom at the screening visit as assessed using a standardised short questionnaire. The individual 'major symptoms' are dyspnoea, increased sputum purulence and increased sputum volume.
- Able to complete questionnaires for health status and symptoms and to keep written diary cards
- Patients must be able to give consent to participate in writing

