12.3.2 Primary outcome analysis

The primary outcome is the time to the next exacerbation within the 90-day study period. This will be analysed using Cox proportional hazards regression and the estimated hazard ratio between the groups will be reported, along with its standard error. A log-rank test will be used to test the primary hypothesis. A Kaplan-Meier plot will be produced. Patients who do not suffer a recurrent exacerbation during follow-up will be treated as censored observations at their end of follow-up time. As analysis is intention to treat, non-compliers will be treated as belonging to the treatment group originally randomised to. Where patients withdraw from follow up, every effort will be made

to ascertain their primary outcome (i.e. date of next exacerbation OR exacerbation-free survival to 90 days) by telephone.

Analysis will be adjusted for a number of important baseline covariates including; sex, exacerbation phenotype, level of symptoms (CAT), levels of CRP, disease severity (FEV), baseline exacerbation frequency in previous year, hospital admission at initial exacerbation.

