Subjects who cease taking their randomised treatment (non-compliers) will continue to be followed up at the end of study visit (day 90), i.e. intention to treat analysis. They will not be "replaced" with a further randomised patient.

It is unlikely that the trial will be stopped prematurely as the study IMP is routinely used for a similar duration to that here. However If a number of SAEs occur that in the opinion of the TSC are deemed unacceptable (if IMP behaving outside the normal safety profile) then the trial will be prematurely stopped.

Compliance to the IMP

- Patients will be asked to complete a daily diary card for the whole period of the trial (i.e. 90 days) to record daily symptoms, patient status, and the need for further therapy. This will also include documentation of IMP compliance, and any missed doses of study medication, during the week of IMP therapy.

Sample size

Over the two centres HES data suggest that it is possible to identify at least 350 hospital admission or ambulatory exacerbations over the 18-month recruitment

period (http://www.hscic.gov.uk/hes). Based on data from the London COPD Cohort, 33% of exacerbating patients have a CRP of 8 or above at 2 weeks. We therefore expect that approximately 115 of the hospital admission or ambulatory exacerbations will be eligible for inclusion due to high CRP. Furthermore, our pilot data suggest that of patients with a normal CRP (<8mg/L), at least 60% of patients report symptoms at day 14; thus of all sampled patients we expect approximately 115+0.6(350-115)=256 to be eligible for inclusion into the trial. Assuming that 90% of eligible patients will agree to take part we initially hoped to randomise 231 patients in total.

Pilot data from our group suggests that at a level of CRP>10mg/l at 14 days, there will be 36% recurrent exacerbations within 50 days. Assuming a constant hazard of exacerbation this translates to around a 55% recurrent exacerbation rate at 90 days. A similar proportion of recurrent exacerbations are seen in the London COPD cohort (for both CRP>10 and CRP<10). An observational database study by Roede et al. (2008) reported a hazard ratio of 0.62 when antibiotics were given in addition to usual treatment.

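### Protocol 12.3.2 lists baseline CRP level as a covariate for the primary outcome, but no SAP primary-outcome model contains it and no reason is given

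*SAP*

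**What the plan says.** The SAP, under Primary outcome analysis, specifies a Cox model stratified by centre and says "We will adjust only for number of exacerbations in previous year and centre in this primary analysis". It then gives three model statements:

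- treatment arm alone;
- arm with site strata and previous-year exacerbations, which it labels a supporting analysis;
- an extended model, surv2, described as "additionally adjusting for baseline covariates age; sex; FEV1% predicted; SGRQ total score; number of exacerbations in previous year" plus further terms.

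One of those further terms is whether the patient entered on symptomatic or inflammatory grounds. It is marked as still to be queried in the variable list and is a placeholder in the code. The SAP confines surv2 to hypothesis generation. The text leaves unclear which of the first two models is primary, but the CRP level is in none of the three.

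Protocol 12.3.2 adjusts for a list that includes "levels of CRP, disease severity (FEV), baseline exacerbation frequency in previous year, hospital admission at initial exacerbation". Protocol 3.2 reports that a "raised serum C-Reactive Protein (CRP) concentration measured 14 days after a first exacerbation is predictive of a second exacerbation within 50 days". Protocol 6.1 makes CRP one of two entry routes: "Measured CRP (C-reactive protein) ≥ 8mg/L AND/OR persistence of one or more major symptom at the screening visit". On the other side, the SAP's Sample size section states "A similar proportion of recurrent exacerbations are seen in the London COPD cohort (for both CRP>10 and CRP<10"), and protocol 12.2.1 says the same. The SAP keeps CRP in its baseline tables.

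**The concern.** A covariate that the protocol lists, ties to eligibility and reports as predictive has left the primary-outcome models without comment. Both documents ask that changes to the statistical plan be described and justified.

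Three things would be at stake if CRP is prognostic. Leaving a prognostic covariate out of a Cox model pulls the estimated hazard ratio towards 1 and loses power. Chance imbalance in CRP stays in the estimate: protocol 8.2 stratifies by site and presence of symptoms, so CRP among symptomatic patients is left to chance. And if the baseline tables then show an imbalance, any CRP-adjusted estimate would be post hoc, which the SAP says it was written to avoid.

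**Working it through.** **1. The SAP's own power figure.** Inputs from the SAP, Sample size: 138 patients, 5% dropout, 90-day exacerbation-free proportion 0.45 on placebo, hazard ratio (HR) 0.46, power 80%. Two-sided 5% is from protocol 12.2.1.

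- Active-arm exacerbation-free proportion: 0.45^0.46 = 0.693.
- Events: 138 × 0.95 / 2 × [(1 − 0.45) + (1 − 0.693)] = 56.2.
- Freedman power: Φ(√56.2 × (1 − 0.46)/(1 + 0.46) − 1.96) = 79.2%. (Schoenfeld gives 82.9%.)

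The 80% reproduces with no covariates, so the sample size does not rest on CRP adjustment.

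**2. Cost of leaving CRP out.** The documents give no CRP effect size, so it is assumed over a range. Simulation: 131 patients (138 × 0.95), treatment HR 0.46 conditional on CRP, placebo 90-day exacerbation-free proportion 0.45, normally distributed (standardised) CRP term, 4,000 trials per row. The yes/no proxy is a clean high-CRP indicator with the share 73/160 implied by protocol 12.2.1 (73 eligible on CRP, 87 on symptoms).

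| Assumed HR per SD of CRP | Power, no CRP | Power, continuous CRP | Power, yes/no proxy | Mean HR, no CRP |
|---|---|---|---|---|
| 1.0 | 80.7% | 80.7% | 80.6% | 0.456 |
| 1.25 | 80.0% | 81.1% | 80.6% | 0.461 |
| 1.5 | 77.8% | 81.1% | 80.8% | 0.473 |
| 2.0 | 72.3% | 82.1% | 78.3% | 0.498 |

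A separate set of 2,000 trials at 1.8 per SD gave 75% without and 82% with CRP, and a mean HR of 0.48 without it. The loss is therefore 0 to about 3 points up to 1.5, about 7 at 1.8 and about 10 at 2.0. Monte Carlo error on one power figure is about √(0.8 × 0.2/4000) = 0.6 points.

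The proxy recovers (80.8 − 77.8)/(81.1 − 77.8) = 91% of the loss at 1.5 and (78.3 − 72.3)/(82.1 − 72.3) = 61% at 2.0.

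**3. Chance imbalance in the share with CRP ≥ 8 mg/L.**

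- Ignoring stratification, with share 73/160 = 0.456: SD of the between-arm difference = √(4 × 0.456 × 0.544/131) = 0.087, so a 95% range of ±17 points.
- With symptom stratification, assuming 60% of high-CRP patients are symptomatic: 0.6 × 73 = 43.8 of 87 + 43.8 = 130.8 symptomatic patients have high CRP, a share of 0.335. Symptomatic patients are 130.8/160 = 0.8175 of entrants, or 107 of 131. SD = 0.8175 × √(4 × 0.335 × 0.665/107) = 0.075, so ±15 points. Symptom-free entrants all have high CRP and contribute nothing.
- Effect on the treatment HR at that extreme, for an assumed HR H for high CRP: [1 + q₁(H − 1)]/[1 + q₀(H − 1)] with q = 0.456 ± 0.073. H = 1.5 gives 1.2645/1.1915 = 1.06; H = 2.0 gives 1.529/1.383 = 1.11.

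For scale, with 56.2 events the standard error of the log HR is about 2/√56.2 = 0.27, so the confidence limits lie a factor of about exp(1.96 × 0.27) = 1.7 either side of the estimate.

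**The case against.** The strongest reply is that the documents' own comparison points to little prognostic value: recurrence was similar above and below CRP 10 mg/L. The predictive finding in protocol 3.2 need not carry over either, because every randomised patient with CRP below 8 must have persistent symptoms, so recovered low-CRP patients are not in the trial. This stands. It is why the range starts at no effect and why the loss may be nil.

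A reader might infer that CRP has been removed from the models altogether. The documents do not support that: surv2 carries an entry-route term whose inflammatory category is CRP ≥ 8, and a clean version would recover much of any loss. As written it cannot be run, it does not say where patients who meet both criteria belong, and it is not in the primary model.

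A reader might also infer that the protocol fixes a continuous or log CRP term in the primary test. It does not. Protocol 12.3.2 speaks only of levels of CRP, does not give the scale, and tests the primary hypothesis with a log-rank test, which has no covariates. Nor is CRP the only change: CAT and exacerbation phenotype are also absent from the SAP models, and sex, FEV1 and hospital admission move to surv2. Restoring CRP alone does not reconcile the two documents.

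On imbalance, ±17 points is an upper figure because it ignores stratification by symptoms, and protocol 12.4 describes stratification by type of inclusion criterion. The ordinary confidence interval already allows for chance imbalance.

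**Conclusion.** The concern holds as a precision and prespecification point. The protocol lists the CRP level, no SAP primary-outcome model contains it, no reason is given, and the only related term is undefined and sits in a hypothesis-generating model.

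The size depends on an assumption that the documents cannot settle. It is negligible if CRP is weakly prognostic in this population and material only if CRP is strong, at 1.8 or more per SD. An imbalance at the 95% limit would move the treatment HR by about 6 to 11% if high CRP carried an HR of 1.5 to 2.0, which is small against the width of the confidence interval.

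It would be wrong to conclude that the primary comparison is invalid or that the stated power is miscalculated. Randomisation protects type I error with or without CRP, and the drift in the HR reflects the difference between a covariate-adjusted and an unadjusted effect. The case for change is the asymmetry: one degree of freedom against about 56 events if CRP proves uninformative, and useful protection if it does not.

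**What to change.** Before unblinding (the SAP lists the arm variable as not yet released):

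- Add baseline CRP as a continuous term to the adjusted primary Cox model and to surv2. The log scale is this review's choice, made because CRP is usually skewed; the protocol does not specify it.
- State which V1 measurement is used. Protocol 8.4 lists both a CRP blood test ahead of the eligibility decision and a laboratory CRP sample whose result may come after treatment starts.
- Keep patients with a missing value in the analysis by simple baseline imputation, using neither arm nor outcome. Otherwise the model would drop them.
- Define the entry-route indicator in surv2, including patients who meet both criteria, and give a short reason for the other covariate changes from protocol 12.3.2.

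The cost is one degree of freedom, a rule for missing values and a few lines of SAP text. CRP is already a scheduled V1 measurement, so no new data are needed.
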